4. PROCEDURES RELATED TO THE STUDY

4.1 Intervention Patients

Patients will be referred by the Pneumology and Infectious Diseases outpatient clinics for a preliminary evaluation of inclusion and exclusion criteria, within the context of scheduled visits for sequelae of SARS-CoV-2 infection. The recruitment phase is divided into an initial screening visit (Visit 1, t-2) to determine if the patient meets the inclusion/exclusion criteria. Following this visit, a

14-day run-in period will be conducted to screen for non-adherent patients, i.e., those who do not show up for the subsequent visit. The patient will return for a visit at 14 days (Visit 2, t0) when randomization will occur, and the patient will be assigned to the treatment or placebo group. The patient will be instructed to take the treatment (supplement or placebo) at the prescribed dosage of two sachets per day for a consecutive and continuous period of four weeks. During this visit, all immunological and microbiological analyses will be performed, including the collection of 20 mL of blood and 1 g of fecal material. The patient will also complete clinical questionnaires to assess the primary and secondary endpoints. The clinical questionnaires will be stored in a deidentified form at the Gastroenterology and Endoscopy Unit, while the biological samples will be shipped and analyzed at the Mucosal Immunology Laboratory of the IEO. Considering the short duration of the study and the lack of literature data demonstrating a clear benefit of VSL#3 on this syndrome, no crossover between study arms is planned under any circumstances. During the study, the use of immunosuppressants or immunomodulators, glucocorticoids, opioids, antidepressants, or anxiolytics at regular and continuous dosages is not allowed. If there is a clinical necessity for antibiotic therapy, it will result in discontinuation of the study. After completing the 28-day treatment period, the patient will return for a visit (Visit 3, t4) where immunological and microbiological analyses will be repeated, and questionnaires will be completed again to evaluate the primary and secondary endpoints. An additional visit with completion of clinical questionnaires will be scheduled 28 days after the end of the treatment (Visit 4, t8) to assess whether any response is maintained at the end of the treatment period.

4.2 Randomization

Randomization will be managed using the REDCap (Research Electronic Data Capture) software. Considering the relatively small number of anticipated patients (n = 96, see dedicated section), we have planned a permuted block randomization with a 1:1 ratio between the placebo and treatment groups. Given the higher expression of the Long-Covid-19 Syndrome in females, randomization will be stratified by sex. We do not anticipate any socio-health or ethical factors that could interfere

with the randomization process to bias patients into one arm over another.

4.3 Blinding

The study participants, healthcare professionals delivering the intervention, and outcome assessors will be blinded to the treatment being administered. Actial Farmaceutica will provide drug and placebo packages that are indistinguishable from each other and will disclose the nature of the two treatments at the end of the study analyses. In the event of serious adverse effects that require hospitalization and the patient's admission, an external collaborator not involved in the study will be informed of the treatment nature through direct contact with Actial Farmaceutica to intervene if necessary.

5. ENDPOINTS

5.1 Primary Endpoint

Demonstration of a statistically significant difference between the placebo group and the treatment group in the scores of the Chalder Fatigue Scale at the end of the treatment period (t4). The Chalder Fatigue Scale is a validated scale used to assess fatigue in the context of CFS/ME [39-41].

5.2 Secondary Endpoints

Demonstration of a statistically significant difference between the placebo group and the treatment group after 4 weeks of treatment (t4) and after an additional 4-week follow-up period (t8; 1 month after the end of treatment), unless otherwise specified, for the following variables:

- Scores of the Chalder Fatigue Scale (t8)
- Hospital Anxiety and Depression Scale (HADS). HADS is a validated scale that quantifies anxiety and depression experienced by the patient [42,43].
- Short Form Health Survey (SF-36). SF-36 is a validated scale that assesses health-related quality of life [44].
- Structured Assessment of Gastrointestinal Symptoms Scale (SAGIS). SAGIS is a validated scale that measures the intensity and impact of gastrointestinal symptoms [45].

- Somatic symptoms of the Symptom Checklist-90 (SCL-90) assessed by the SCL 12. SCL-90 is a validated questionnaire that assesses psychological distress in individuals [46-52,54].
- Karnofsky Performance Status (KPS) Scale. KPS is a validated scale consisting of 11 points that describes the overall functional status of a patient on a range from 100% (no evidence of disease, no symptoms) to 0% (death) [49,50,51,52].
- Visual Analog Scale (VAS) rating of the patient's overall health status by the examining physician.
- Serum expression of cytokines (IL-2, IL-7, IL-15, IL-10, IL-33, IL-4, IL-5, IL-13, IL-1a, IL-1b, IL-1Ra, IL-12p70, IFNa, IFNb, IFNg, TNFa, TRAIL, GRZb, IL-6, IL-17A, IL-17F, IL-22, and IL-23), chemokines (CXCL1 (GROa), CXCL2 (GROb), CXCL8 (IL-8), CXCL10 (IP-10), CX3CL1 (Fraktalkine), CCL2 (MCP-1), CCL3 (MIP1a), CCL4 (MIP-1b), CCL5 (Rantes), CCL11 (Eotaxin), CCL19 (MIP3b), and CCL20 (MIP3a)), growth factors (FLT3L, IL-3, G-CSF, GM-CSF, TGFa, EGF, PDGFaa, PDGFab/bb, VEGF, and FGF basic), and immune activation markers (CD40L and PDL1).
- Variation in the bacterial component of the fecal microbiota in terms of alpha and beta diversity and correlation of these parameters with clinical response on fatigue.

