2.2 Secondary Objective(s)

1. To determine if this high-concentration probiotic formulation can improve scores of anxiety, depression, quality of life, gastrointestinal symptoms, cognitive deficits, performance, psychological distress, and clinical evaluation of the study patients.
2. To assess the immunological profile of inflammation markers in blood and bacterial species in feces in patients treated with VSL#3® compared to patients treated with a placebo. Any differences before and after treatment will be identified.

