7. STATISTICAL ANALYSIS

7.1 Sample Size

Assuming a placebo effect of 30% reduction in the primary outcome (fatigue assessed by Chalder Fatigue Scale - Likert 0-33), a statistical power of 80% with a significance level of 0.05 (two-tailed),

we estimate that 42 patients per arm are needed to detect a 60% efficacy of the probiotic in reducing the same parameter. This reduction, if confirmed, would have significant clinical relevance, indicating a substantial efficacy compared to placebo. Considering a dropout rate of 15%, we believe that recruiting 48 actual patients per arm is necessary to demonstrate this efficacy.

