7.2 Data Analysis

Both intention-to-treat and per-protocol analyses will be conducted. Depending on the distribution of the data, Student's t-test or Wilcoxon Mann-Whitney test will be used for continuous variables, and Chi-square test or Fisher's exact test for categorical variables. Relationships between multiple variables will be assessed using linear or logistic regression tests based on the nature of the available data. Statistical analysis will be performed using the RStudio software (R Core Team, 2020) and Stata software (StataCorp, 2013). No interim analyses are planned due to the short duration of the study and the relatively small number of enrolled patients.

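### The 47-protein serum panel carries a significance criterion with no multiplicity control or exploratory label; one test per protein at 0.05 would give 2.35 expected false positives if nothing differs

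*Combined protocol and SAP*

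**What the plan says.** Section 5.2 opens its list with "Demonstration of a statistically significant difference between the placebo group and the treatment group after 4 weeks of treatment (t4"). The same sentence then sets a second default time for every listed variable: "after an additional 4-week follow-up period (t8; 1 month after the end of treatment), unless otherwise specified". The serum bullet in that list begins "Serum expression of cytokines" and goes on to chemokines, growth factors and immune activation markers, each named.

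The matching objective, 2.2 item 2, reads "To assess the immunological profile of inflammation markers in blood and bacterial species in feces", comparing VSL#3 with placebo, and adds "Any differences before and after treatment will be identified".

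Section 7.2 is the whole analysis plan. For this kind of variable it says that Student's t-test or the "Wilcoxon Mann-Whitney test will be used for continuous variables", with regression for relationships between variables. It plans both intention-to-treat and per-protocol analyses. It mentions no correction for multiple tests, no testing order, no global test and no exploratory status for any endpoint.

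The only significance level in the documents is in 7.1, for the primary outcome: "a statistical power of 80% with a significance level of 0.05 (two-tailed").

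Section 4.1 describes blood and stool analyses at t0 and t4, and questionnaires at t8.

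**The concern.** Section 5.2 holds the serum panel to the same kind of criterion that 5.1 sets for the primary endpoint: a significant difference between arms counts as a demonstration. With dozens of proteins and no rule for reading them together, some are likely to cross 0.05 by chance. A product with no effect on any marker could then be reported, in line with the plan, as having a demonstrated effect on one or more.

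What is at stake is the mechanistic claim under objective 2.2 item 2. Proteins named in advance do allow a reader to correct for the number of tests, but only if every p-value is published, and the plan does not say that it will be.

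**Working it through.** The plan gives no count of tests and no error rate for the panel, so there is no figure of its own to reproduce here. The 42 patients per arm in 7.1 enters only the power calculation in step 4.

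**1. Count of proteins (5.2).** 23 cytokines + 12 chemokines + 10 growth factors + 2 activation markers = 47, with no duplicates and PDGFab/bb counted once. Counting it twice would give 48 proteins and 48 × 0.05 = 2.40.

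**2. Expected false positives.** Assumptions: one between-arm test per protein, at t4, in one analysis set, two-sided 0.05, no true effect. Expected number = 47 × 0.05 = 2.35. Expectations add regardless of dependence, so this holds at any correlation.

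**3. Chance of at least one.** If independent: 1 − 0.95^47 = 0.910. The documents give no correlation between markers, so a range is shown, using normal test statistics with a common pairwise correlation. The last column is the chance of any rejection under Benjamini-Hochberg at 5% (simulated), again with no true effect.

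| Assumed correlation | At least one false positive | Median count | 95th percentile of count | Any rejection under Benjamini-Hochberg |
|---|---|---|---|---|
| 0 | 91% | 2 | 5 | 5.0% |
| 0.3 | 79% | 2 | 8 | 4.6% |
| 0.5 | 61% | 1 | 10 | 3.7% |
| 0.7 | 40% | 0 | 13 | 2.6% |
| 0.8 | 29% | 0 | 15 | 2.2% |

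As correlation rises, a false positive becomes less likely, but false positives come in larger clusters, which could look like a coherent immune response.

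**4. Cost of correcting.** Noncentral t, 42 per arm, 80% power. The worst case is a single truly different marker, which has to meet about 0.05/47 = 0.00106.

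- Unadjusted, at 0.05: 0.62 SD is detectable.
- Unadjusted, at 0.00106: 0.93 SD is detectable. Ratio 0.93/0.62 = 1.5. Power at 0.62 SD falls from 80% to 30%.
- If 5, 10 or 20 of the 47 truly differ (independent markers, simulated), Benjamini-Hochberg brings the detectable difference to about 0.82, 0.77 or 0.71 SD.

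**5. Adjustment for t0.** The detectable difference is multiplied by about √(1 − r²), where r is the t0–t4 correlation. The documents do not give r, so it is assumed.

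| r | Uncorrected (0.05) | Corrected (0.00106) | Ratio |
|---|---|---|---|
| 0.3 | 0.59 SD | 0.89 SD | 1.5 |
| 0.5 | 0.54 SD | 0.80 SD | 1.5 |
| 0.7 | 0.44 SD | 0.66 SD | 1.5 |
| 0.8 | 0.37 SD | 0.56 SD | 1.5 |

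Baseline adjustment helps both columns equally, and the ratio does not move.

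**The case against.** The strongest reply is that the documents never say 47 separate tests will be run. Section 5.2 puts the panel in one bullet, 2.2 speaks of a profile, and the 0.05 level is stated only for the primary outcome. That is right as far as it goes: 2.35 describes one analysis that the plan permits and is not a figure the plan commits to. But 7.2 names no global test and offers only two-group tests or regression for continuous variables, and 0.05 is the only level given. One test per protein is therefore the natural reading.

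It can also be said that secondary biomarkers are commonly understood as exploratory, and that no later decision in the protocol depends on them. This limits the weight of the point. It does not answer it, because 5.2 asks for a demonstration of significance and nothing calls the panel exploratory.

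A reader might infer more than the documents support, in three ways.

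- *That the trial's main conclusion is at risk.* It is not. The primary endpoint is one scale at one time (5.1), and its error rate does not depend on the serum tests.
- *That 91% is the false-positive risk.* It is the value under independence only. The correlation is unknown, and at 0.8 the risk is about 29%.
- *That the t4 and t8 default in 5.2 doubles the panel to 94 tests.* The serum and microbiota bullets (the latter starts "Variation in the bacterial component of the fecal microbiota in terms of alpha and beta diversity") state no time, so the default literally covers them. But 4.1 describes sampling at t0 and t4 only, and 2.2 speaks of before and after treatment. Together they point to t4. This is a wording matter that the Gantt chart or appendix, neither visible here, may settle.

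**Conclusion.** The concern holds, and the plan should be changed. A significance criterion applies to 47 named proteins with nothing to govern how the 47 results are read together. The size is 2.35 expected false positives when there is no true effect, and a chance of at least one between 29% and 91% over assumed correlations from 0.8 down to 0.

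This rests on two inferences, one test per protein and a 0.05 level, and on counting a single comparison at t4 in a single analysis set. Testing in both the intention-to-treat and per-protocol sets, or adding before-and-after tests, would increase the number of tests.

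The matter is confined to a secondary, mechanistic objective. It would also be wrong to conclude that t0 adjustment pays for the correction: compared like for like, the worst-case penalty stays at about 1.5-fold at every t0–t4 correlation examined.

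**What to change.** In 5.2 and 7.2, choose one of the following for the serum panel.

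- Compare the 47 proteins between arms at t4 with the false discovery rate controlled at 5% (Benjamini-Hochberg) across the panel, and report all 47 results.
- Label the panel exploratory, remove the significance criterion for it, and report between-arm estimates with 95% confidence intervals.

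As a separate improvement under either option, adjust each comparison for the t0 value, which 4.1 already plans to collect. It sharpens the estimates with or without a correction.

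As a side note, reconcile the t4 and t8 default in 5.2 with 4.1 and 2.2 for the serum and microbiota bullets, after checking the Gantt chart and appendix.

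The cost is a sentence in each section and a few lines of code, with no new samples. The first option loses power for an isolated marker: 0.62 to 0.93 SD unadjusted in the worst case, and less if several markers truly differ. The second avoids that loss but gives up any claim of a demonstrated marker effect.

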symptom, with fatigue being the main one (53.1%) [32]. In a study conducted using an online platform, Goërtz et al. demonstrated that in a cohort of 2113 patients (including patients with a confirmed or suspected diagnosis of COVID-19), the number of symptoms experienced 79 days from the onset of the illness had significantly reduced, but at the same time, only 0.7% of patients were symptom-free. Once again, fatigue was the most reported symptom (87%) [33]. A study by Townsend et al. from Ireland, involving 128 patients, approximately half of whom were hospitalized for COVID-19, evaluated after a median time of 72 days, showed that only 42% of these patients had a health status comparable to that before the infection. 52% of the subjects met the diagnostic criteria for fatigue, with Chalder Fatigue Scale (ChFS) scores similar to those of patients with CFS/ME. Surprisingly, the state of fatigue does not seem to be correlated with the clinical severity of SARS-CoV-2 infection or the presence of inflammatory changes (e.g., white blood cell count, neutrophil count, neutrophil-to-lymphocyte ratio, and levels of PCR, LDH, IL-6), suggesting a more subtle etiopathogenic mechanism in line with other observations in CFS/ME [34]. Another Norwegian study observed the prevalence of fatigue in a cohort of non-hospitalized SARS-CoV-2 positive patients, using the ChFS via postal survey conducted at a distance from the diagnosis of COVID-19. The 458 enrolled patients responded after a median time of 117 days from SARS-CoV-2 infection, and 46% showed a ChFS score (in dichotomous mode) compatible with clinically significant fatigue, while the Likert Scale score of the same scale differed significantly from that obtained from a cohort of healthy subjects [35]. Finally, in our own case series of 164 patients studied five months after SARS-CoV-2 infection, compared to a control group of 183 subjects, the relative risk of CFS was increased by 2.24.

VSL#3® is a patented high-concentration blend (450 billion bacterial units) of live and lyophilized lactic acid bacteria and bifidobacteria, belonging to eight different strains (one strain of *Streptococcus thermophilus* BT01; three strains of *Bifidobacteria*: *B. breve* BB02, *B. animalis* subsp. *lactis* BL03 (formerly known as *B. longum* BL03), and *B. animalis* subsp. *lactis* BI04 (formerly known as *B. infantis* BI04); four strains of *Lactobacilli*: *L. acidophilus* BA05, *L.*

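### The only post-baseline stool is taken as dosing ends and product bacteria are not separated from resident flora, so a diversity difference at t4 may show only that the product was swallowed

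*Combined protocol and SAP*

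**What the plan says.** Section 1.1 describes the product as a "patented high-concentration blend (450 billion bacterial units) of live and lyophilized lactic acid bacteria and bifidobacteria, belonging to eight different strains". The named strains cover seven species, because two of them are both *B. animalis* subsp. *lactis*. Section 4.1 has patients take "two sachets per day for a consecutive and continuous period of four weeks".

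Section 4.1 also sets the sampling. Visit 2 (t0) has the baseline analyses, "including the collection of 20 mL of blood and 1 g of fecal material". The next sample comes when dosing is complete: "After completing the 28-day treatment period, the patient will return for a visit (Visit 3, t4) where immunological and microbiological analyses will be repeated". No interval between the last sachet and this stool is stated. The last visit is described with questionnaires only: "An additional visit with completion of clinical questionnaires will be scheduled 28 days after the end of the treatment (Visit 4, t8").

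Section 5.2 defines the endpoint as "Variation in the bacterial component of the fecal microbiota in terms of alpha and beta diversity and correlation of these parameters with clinical response on" (last word: fatigue). Its opening sentence places all secondary variables "after 4 weeks of treatment (t4) and after an additional 4-week follow-up period (t8; 1 month after the end of treatment), unless otherwise specified", and the microbiota item carries no exception.

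Section 7.2 names t-tests or rank tests, chi-square or Fisher tests, and regression. It names no microbiome method and does not say how product taxa are handled. Section 3.3 rules out other probiotics during the trial.

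**The concern.** The background argues that infection alters the patient's intestinal flora and that this alteration may contribute to fatigue. The microbiota endpoint is the trial's link between that argument and the clinical result. At t4 the active arm has just finished swallowing a concentrated bacterial blend. If those organisms or their DNA are in the stool, they count towards richness, diversity and between-sample distance. Because other probiotics are barred, they also largely mark the active arm.

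Two results are then hard to interpret. A significant arm difference cannot be assigned to a changed resident community rather than to passage of the product. The correlation with fatigue response, if pooled over arms, can arise without any link inside either arm: product taxa shift diversity in one arm, and any arm difference in fatigue response does the rest.

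**Working it through.** **Inputs from the documents.** Eight strains in seven species (1.1); stool at t0 and t4 (4.1); two-sided 0.05, 80% power, 42 per arm needed and 48 recruited with 15% dropout (7.1); t-test for continuous variables (7.2). No sample size is stated for the microbiota endpoint, so the plan's arm size is used.

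**The plan's arm size.** Reading 30% and 60% as two proportions, with mean 0.45:

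n = [1.960·√(2·0.45·0.55) + 0.842·√(0.30·0.70 + 0.60·0.40)]² / 0.30² = (1.379 + 0.565)² / 0.09 = 42.

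This matches the plan. With 15% dropout, 48 × 0.85 = 40.8, so 41 per arm were simulated.

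**Bray-Curtis, exact.** Let x be the resident relative abundances and q the product's, with no taxa in common, and let the product take share p of the sample. Then y = (1−p)x + pq, and

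BC(x, y) = ½Σ|x − y| = ½(p·1 + p·1) = p.

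The resident community has not changed, yet the distance equals the product share.

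**Shannon, exact.** With residents at H₀ and product at H_q, the change is p(H_q − H₀) + h(p), where h(p) = −p ln p − (1−p) ln(1−p). Take H₀ = 3.5 (assumed).
- One product taxon (H_q = 0): at p = 10%, −0.350 + 0.325 = −0.025; at p = 20%, −0.700 + 0.500 = −0.20.
- Seven equal taxa (H_q = ln 7 = 1.946): at p = 10%, −0.155 + 0.325 = +0.17.

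The direction is not fixed.

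**Simulation, no effect on resident bacteria.** Assumptions not in the documents: 200 resident taxa, each present with probability 60%; 20,000 reads; seven product species absent at t0 and in placebo; product share log-normal across active patients with the median shown (the mean is e^0.5 = 1.65 times the median, before a cap at 60%). Tests were a t-test for alpha diversity and a permutation test for beta diversity, with 150 trials per setting. The Monte Carlo standard error at 5% is √(0.05·0.95/150) = 1.8 points. Entries are the percentage of trials declaring an arm difference, with product kept / product removed and the rest renormalised.

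| Index | No product | 0.1% | 1% | 5% | 10% |
|---|---|---|---|---|---|
| Jaccard | 4 / 5 | 100 / 5 | 100 / 3 | 100 / 9 | 100 / 3 |
| Bray-Curtis | 6 / 5 | 7 / 6 | 22 / 7 | 100 / 4 | 100 / 6 |
| Richness at t4 | 3 / 3 | 76 / 4 | 87 / 4 | 72 / 9 | 62 / 12 |
| Change in richness | 4 / 4 | 94 / 7 | 100 / 5 | 97 / 8 | 81 / 27 |
| Shannon at t4 | 5 / 5 | 6 / 6 | 7 / 5 | 23 / 7 | 39 / 5 |
| Change in Shannon | 3 / 3 | 3 / 5 | 9 / 7 | 35 / 4 | 59 / 7 |

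The active arm's mean excess gain in richness was about 5 to 7 taxa, close to the seven species ingested. Using the t0 sample as baseline does not remove the artefact; for richness it makes it easier to detect. Removing product taxa returns most tests to near 5%. The exception is richness at high share (12%, and 27% for change), because filtering leaves the active arm fewer reads. Rarefying to equal depth removes that imbalance.

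**Sensitivity to the assumed community.** For Bray-Curtis with 42 per arm and a mean share of 2%, other assumed levels of between-patient variation gave rejection from 34% to 98%. In one such set, 34%, 76% and 93% fell to 18%, 38% and 54% when the same species already averaged 2% in both arms. At a mean share of 5%, rejection was 76% to 100%.

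**The case against.** Arms are randomised, so any t4 difference is an effect of treatment, and whole-community diversity is a legitimate description of what the product does to stool. Objective 2 in section 2.2 asks about bacterial species in faeces by arm and before versus after treatment. It does not restrict itself to resident flora, and section 5.2 does not claim to show correction of dysbiosis. The administered species may themselves be the mechanism; section 1.1 cites a *Bifidobacterium* study with symptom benefit. Filtering would discard them, together with any real change in resident members of those species. All of this stands. It argues for keeping the whole-community result, not for leaving the two sources unseparated.

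The rates depend on assumptions that the documents cannot settle: product share, sequencing depth, taxonomic resolution, community structure, and a permutation test that 7.2 does not name. This also stands, and the rates are illustrative only.

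A reader might infer more than the documents support:
- That stool is sampled only at the end of dosing. A t0 sample exists, although it does not solve the problem.
- That the plan expressly computes diversity on all bacteria and rules out a later stool. The first is the plain reading of a text that states no filter. On the second, 5.2 nominally includes t8 while 4.1 schedules no stool there.
- That alpha diversity would appear to improve. Richness tends to rise, but Shannon moves little and can fall.

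**Conclusion.** The point holds as a gap in specification. With the only scheduled post-baseline stool at the end of dosing and no handling of product taxa, the endpoint as written cannot distinguish passage of the product from a changed resident community, and a pooled fatigue correlation shares the weakness.

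The size is index-specific. Under the stated assumptions, Jaccard and richness are affected at a median share of 0.1%, Bray-Curtis from about 1% to 5%, and Shannon only at the higher shares. Every figure shrinks if the product species are already resident, and the true share is unknown.

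It would go too far to call any t4 difference an artefact, or to say that the filtered analysis must replace the whole-community one: objective 2 is worded broadly enough to include product species. This is one item in a long secondary list. The primary Chalder comparison at t4 is unaffected.

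**What to change.** In sections 5.2 and 7.2, before diversity is analysed by arm:

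- Keep the whole-community comparison at t4. Beside it, pre-specify the same alpha- and beta-diversity analysis after removing reads assigned to the seven species of the eight product strains and renormalising, with rarefaction to equal depth for richness.
- Name the diversity indices, the beta-diversity test and the taxonomic resolution.
- Analyse the correlation with fatigue response on the filtered community, within arm or adjusted for arm.
- Report product taxa separately as evidence of exposure.
- Rest any conclusion about altered resident microbiota on the filtered result.
- Reconcile 5.2 (t4 and t8 by default) with 4.1 (questionnaires only at Visit 4) for this endpoint.

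The filtered analysis needs no new sample, only extra processing of data already planned. Filtering also removes resident members of the same species and needs adequate taxonomic resolution; with genus-level data whole genera would be lost. Showing both results covers this.
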